A competing risks sensitivity analysis will be conducted using these two methods. More specifically, Gray's test for subdistribution hazards will be used for comparing the cumulative incidences of each secondary outcome by treatment group and the proportional subdistribution hazards model proposed by Fine & Gray will be used to estimate the treatment effects (subdistribution hazard

ratios). The methodologies described above are available in and will be implemented through the R *cmprsk* package.

Gray's test will be compared with the logrank test for the treatment effect. We will also compare the subdistribution hazard from Fine-Gray model to the cause specific hazard from the Cox model to improve understanding of the treatment effect. A cumulative incidence curve will be compared to Kaplan-Meier curve.

- *Analysis of Secondary Outcomes: Cognitive Decline (Modified MMSE Score)*

To determine whether pioglitazone, compared to placebo, reduces the risk for cognitive decline, as measured by the modified MMSE score, a longitudinal analysis will be done. Repeated measures of the modified mini mental state exam will be analyzed by mixed model methods adjusted for the study design. In addition, secondary analyses will be conducted comparing participants who decline from a normal modified MMSE score ( $\geq 90$ ) to an exit score of  $< 78$  by treatment groups using a logistic model.

The primary analysis will be based on an analysis of covariance mixed model approach using maximum likelihood estimation assuming missing data are missing at random. All participants with available data will be included in the model. Initially, we will determine the most appropriate covariance structure for the repeated outcomes and then fit the mean model. Treatment by time interactions will be examined to determine whether the treatment effect is constant over time. If there is evidence of an interaction ( $p < 0.05$ ), the data will be analyzed by time point.

- *Sensitivity Analysis for Cognitive Data*

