The mixed effects model based on maximum likelihood estimation is unbiased if missing data are unrelated to outcomes, i.e., if the data are considered missing at random (MAR) or missing completely at random (MCAR). Nevertheless, because it is not always known whether missing data are ignorable and because missing observations have the potential to alter the results of analyses, the pattern of missing data and dropouts will be examined among the two treatment arms. We will also examine whether the outcome is related to missingness by using logistic regression models to determine if the outcome measure at the follow-up time preceding the missed visit predicts the missing value and if baseline value predicts non-intermittent missing (i.e., missing last expected score). If there are no systematic differences between those with and without missing data, the data can be considered to be observed (and missed) at random. If the outcome measure is predictive of missing data, it would indicate that the missing data are potentially not MAR or MCAR. Also, if there are no covariates predictive of missing data it would be another indication that the data may likely be MAR. If the missing data are determined to be possibly non-ignorable and there is a reasonable likelihood that the conclusions could be altered by the missing information, sensitivity

analyses will be considered to determine the impact of missing information on the treatment comparisons including the approach proposed by Carpenter et al. (e.g., multiple imputation that reflects the behavior of the missing data or including variables that are predictive of missingness in the model).

SAS code for all completed analyses is available upon request.

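### The cognitive missing-data section misdefines MAR, and its trigger for sensitivity analysis rests on regressions that cannot separate MAR from MNAR

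*SAP*

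**What the plan says.** In the SAP, Analytical Plans, the section on cognitive decline fits a repeated-measures mixed model by "maximum likelihood estimation assuming missing data are missing at random". The next section, Sensitivity Analysis for Cognitive Data, says this model is "unbiased if missing data are unrelated to outcomes, i.e., if the data are considered missing at random (MAR) or missing completely at random (MCAR").

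It then sets out two logistic regressions. One is to "determine if the outcome measure at the follow-up time preceding the missed visit predicts the missing value". The other asks whether the baseline score predicts a missing final score. Results are read as follows:

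- Null result: "If there are no systematic differences between those with and without missing data, the data can be considered to be observed (and missed) at random".
- Positive result: "If the outcome measure is predictive of missing data, it would indicate that the missing data are potentially not MAR or MCAR".
- Covariates: "if there are no covariates predictive of missing data it would be another indication that the data may likely be MAR".

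Further analyses are to be considered if two conditions are met: the missingness is judged possibly non-ignorable, and the conclusions might plausibly change. The examples are multiple imputation that mirrors how the missing data behave, and adding predictors of missingness to the model. Separately and without condition, the pattern of missing data and dropout is to be examined in the two arms.

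**The concern.** Missingness unrelated to outcomes is in substance MCAR. Under MAR it may depend on any score or covariate that was observed, and that allowance is the main reason to choose a likelihood mixed model. By equating the two, the SAP treats ordinary MAR behavior as a warning and the absence of an association as reassurance.

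The error then feeds the trigger. A departure that biases the mixed model is dependence on the score that was not seen, given those that were. Neither regression contains that score.

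The case that could be missed is a realistic one here. Under Secondary Objectives the SAP expects pioglitazone to slow cognitive decline by preventing strokes, including clinically unapparent ones. A stroke between two examinations could cause both an abrupt fall and a missed examination. Earlier scores might not predict it, and by the trial's own hypothesis its frequency differs by arm. A null regression would then leave the MAR analysis unchallenged.

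**Working it through.** The SAP gives no figure on this point, so there is none to reproduce. The check is one of logic, illustrated by simulation.

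**Step 1: definitions.** Let R be the indicator that the score Y_j is missing.

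- MCAR: P(R) depends on no score.
- MAR: P(R) may depend on observed scores and covariates.
- MNAR: given those, P(R) still depends on the unseen Y_j.

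The SAP's regression is logit P(R) = a + b·Y_(j−1), or the same with the baseline score. Testing b = 0 can reject MCAR. What separates MAR from MNAR is the coefficient of Y_j, which is not in the model.

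**Step 2: when the regression fires under MNAR.** With correlation ρ between visits and standardized scores, Y_j = ρ·Y_(j−1) + residual. The effect of Y_(j−1) implied by each mechanism is:

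- Dropout on the residual (new decline that the past does not predict): none.
- Dropout on the current score Y_j: proportional to ρ, so 0.6 when ρ = 0.6.
- Dropout on the change Y_j − Y_(j−1): proportional to ρ − 1, so −0.4 when ρ = 0.6.

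The regression is therefore silent in the first case and tends to fire in the other two, less strongly in the third.

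**Step 3: one follow-up visit.** Assumptions, none from the SAP: N = 2000, ρ = 0.6, about 10% missing, 400 runs per cell, dropout log-odds of 0.3, 0.5 and 1.0 per SD, test at 0.05.

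| MNAR mechanism | Regression fires at 0.3 / 0.5 / 1.0 |
|---|---|
| Residual | 5% / 3% / 5% |
| Current score | 66% / 97% / 100% |
| Change | 37% / 76% / 100% |

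The bias in the arm mean was similar for all three mechanisms: about 0.02, 0.03 and 0.06 SD. Under MAR dropout on the preceding score the regression fired in 98 to 100% of runs, with no bias.

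**Step 4: treatment contrast over repeated visits.** Assumptions: 4000 participants 1:1 (SAP, Study Design). The rest are not from the SAP: baseline plus five annual scores, SD 8 points, AR(1) correlation 0.3, 0.5 or 0.7, true difference 0, monotone dropout with 35 to 49% missing the last score, 60 runs per cell. Fit: maximum likelihood with arm-by-time means and a common unstructured covariance.

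| Dropout mechanism | Preceding-score test fires | Baseline test fires | Bias in contrast (points) |
|---|---|---|---|
| MCAR | 3–8% | 3% | −0.02 to 0.02 |
| MAR, preceding score (both arms, or one arm only) | 100% | 100% | −0.04 to 0.01 |
| MNAR, residual, one arm | 7% | 2–7% | 2.64 to 3.84 |
| MNAR, current score, one arm | 100% | 82–100% | 2.20 to 2.46 |
| MNAR, current score, both arms alike | 100% | 88–100% | −0.01 to 0.04 |

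The Monte Carlo standard error of the bias is 0.03 to 0.05 points.

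**Step 5: reading the table.** Rows two and four give the same signal on the preceding-score test, yet the model is unbiased in one and biased in the other. Rows one and three both give roughly the nominal rate, yet the model is unbiased in one and biased in the other. Neither a positive nor a null result says whether the mixed model is valid.

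**The case against.** A reader might infer that the rule has MAR backwards and stays silent whenever the model is biased. The documents and the check do not support that. Silence needs missingness driven only by what past scores do not predict. If a low current score causes the missed visit, the preceding score usually predicts missingness and the rule does prompt further analysis.

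A reader might also take the simulated sizes as the error in the trial's result. They are not. The hundredths of an SD in Step 3 are bias in one arm's mean. The 2 to 4 points in Step 4 require MNAR dropout in one arm only, a steep dropout slope and nearly half of the last scores missing. The SAP gives neither a missing fraction nor a mechanism. With the same mechanism in both arms the contrast was essentially unbiased.

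The SAP is also more cautious than a mechanical gate. It sets no significance threshold for these regressions, hedges its inferences, adds a second condition, and looks at dropout by arm in any case. A false alarm under MAR does little harm. Adjudicated strokes are recorded, so adding them as predictors could recover part of the stroke-related missingness. The multiple imputation might be meant as an MNAR method.

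All of this limits the severity. It does not make the inferences correct. Dropout by arm, like the regressions, is observed data and cannot show MNAR. Adding predictors still relies on MAR and cannot capture unapparent strokes. The imputation is described too loosely to tell what it assumes, and it need not be run.

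**Conclusion.** Wrong as written, moderate severity. The section misdefines MAR, and all three readings of the diagnostics fail: a positive score regression as a sign against MAR, a null one as showing MAR, and the absence of predictive covariates as support for MAR. The regressions test MCAR against not-MCAR. The trigger can fire when the mixed model is valid and, under some MNAR mechanisms, fail to fire when it is biased.

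This conclusion rests on the definitions. The simulated sizes rest on assumed dropout models, and no size for this trial can be taken from the SAP. Bias in the treatment contrast arises only if the MNAR mechanism differs by arm; this was checked with a true difference of zero. The point touches one of six secondary outcomes. The primary endpoint is unaffected, and the main cognitive model is a standard choice that can stay.

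**What to change.** 1. Replace the opening statement with one saying that the maximum-likelihood mixed model is valid under MAR, where missingness may depend on observed scores and on covariates in the model. Delete the sentences that read the regressions, or the absence of predictive covariates, as evidence for or against MAR.
2. Keep the logistic regressions and the comparison of dropout by arm as descriptive, and use them to choose auxiliary variables for imputation.
3. Pre-specify one MNAR sensitivity analysis of the 3MS treatment comparison and run it whatever the regressions show. Delta-adjusted or pattern-mixture multiple imputation would serve, with delta allowed to differ by arm and its range fixed before unblinding. Other MNAR methods are acceptable if fully specified.

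The cost is revised SAP wording and one extra analysis on data already planned. No new data are needed, and the main cognitive model does not change.

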## **Appendix 1: Endpoint Definitions**

### **A. Protocol Endpoint Definitions (Primary and Secondary Outcomes)**

Fatal or non-fatal stroke or fatal or non-fatal MI were selected as the primary outcomes for the IRIS trial for three main reasons. First, they are the major vascular events contributing to morbidity and mortality after an initial ischemic stroke or TIA. Second, they have both been associated with insulin resistance, and treating insulin resistance may reduce risk for each of them. Third, stroke and MI can be detected and verified with a high degree of accuracy. In addition, we will examine several endpoints other than stroke and MI as secondary endpoints. Definitions for all primary and secondary endpoints are as follows:

#### **Stroke**

For purposes of this trial, stroke is an acute neurological event with focal signs or symptoms lasting at least 24 hours which represent a focal loss of brain function that can be attributed to a disturbance in one vascular distribution and for which no other cause is found. In addition, there must be at least a one-point increase in the NIH stroke scale in a previously normal section, or an appropriate new or extended abnormality seen on CT or MRI. IRIS will count non-traumatic intracerebral and subarachnoid hemorrhage as outcomes in addition to ischemic events. Subdural and epidural hematoma are not included as part of the primary stroke outcome. A stroke is classified as fatal if death occurs within 30 days or if, in the opinion of the neurology review committee, death is a direct result of a physiological consequence of a stroke event.

#### **Myocardial Infarction**

Acute myocardial infarction will be diagnosed according to criteria modified from the 2000 Consensus Conference of the European and American Colleges of Cardiology. MI events will be diagnosed based on patient symptoms and electrocardiogram changes, in conjunction with contemporary biochemical markers of myocardial necrosis (troponin or CK). Both acute ST segment elevation and non-ST segment elevation MI will be combined as an outcome. An acute, evolving, or recent non-fatal MI will be diagnosed in the presence of a typical rise and gradual fall (troponin) or more rapid rise and fall (CK-MB) of biochemical markers of myocardial necrosis with at least one of the following: a) ischemic symptoms, b) development of pathologic Q waves on the ECG, c) ECG changes indicative of ischemia (ST segment elevation or depression), d) coronary artery intervention (e.g., angioplasty), e) angiographic findings indicative of unstable plaque or thrombus in a coronary artery, or f) cardiac imaging (perfusion or echocardiogram) suggestive of MI. Criteria for biochemical markers depend on whether the event was (a) spontaneous, or in setting of (b) cardiac catheterization, angioplasty or stenting, or (c) CABG. Biochemical markers will be considered indicative of necrosis when the CK-MB exceeds (a) 1.5, (b) 3.0 and (c) 5.0 x ULN, respectively, or troponin concentration exceeds (a) 2.0, (b) 5.0, and (c) 10 x ULN, respectively. For participants who do not seek medical care at the time of acute symptoms, a recent non-fatal MI will be diagnosed in the presence of a history of ischemic symptoms and new Q waves on ECG or imaging data clearly indicative of new, focal myocardial damage.

A fatality will be classified as “fatal MI” according to criteria from the Air Force/Texas Coronary Atherosclerosis Prevention Study (AFCAPS/TexCAPS), which requires that there be no non-cardiac cause of death and one of the following: death within 30 days from the onset of symptoms of a definite acute myocardial infarction; witnessed unexpected sudden cardiac death within 1 hour of symptoms; death occurring > 1 hour but < 24 hours after collapse; and unwitnessed and unexpected death that is presumed to be sudden (in this case, there must be confirming autopsy data or, preceding history of CHD events or symptoms).

### **Acute Coronary Syndrome/Unstable Angina**

Acute coronary syndrome (unstable angina, fatal or non-fatal myocardial infarction) are a secondary outcome. The diagnosis of unstable angina will be based on the well-defined criteria from the AFCAPS/TexCAPS study. This diagnosis requires the absence of a diagnosis of myocardial infarction and the presence of new-onset, accelerated exertional or rest chest pain (anginal in quality) lasting > 5 minutes and at least one of the following: mildly elevated troponin values (<2 x upper limit of normal), new or presumably new ST segment deviation >0.5mm in 2 or more leads, T-wave inversion >3mm in 3 leads, left bundle branch block, or abnormal stress testing. Abnormal stress testing is defined as >1mm horizontal or down-sloping ST-segment depression in two or more leads with evidence of abnormalities in stress imaging or coronary angiography as described below (if imaging or angiography is obtained).

Stress imaging evidence:

- Perfusion imaging (MIBI or thallium): A reversible perfusion defect with exercise or pharmacologic stress (adenosine, dipyridamole, dobutamine) imaging; or
- Echocardiography: An inducible regional wall motion abnormality after exercise or pharmacologic stress.

Angiographic evidence:

- >70% stenosis in the LAD, circumflex, or RCA or one of their major branches, or > 50% left main coronary artery stenosis.

### **Diabetes Mellitus**

Diabetes mellitus will be classified based on 2004 American Diabetes Association guidelines. According to these guidelines diabetes is diagnosed when one of three conditions is met: 1) the value of two fasting glucose measurements equal or exceed 126 mg/dl, 2) two random plasma glucose equals or exceeds 200 mg/dl in the presence of typical symptoms of diabetes, or 3) the plasma glucose equals or exceeds 200 mg/dl two hours after a 75 gram oral glucose load, confirmed on a repeat test. In practice, the oral glucose tolerance test is rarely used. For this reason and to reduce the burden of participating in the trial, we will classify a participant as having diabetes if one of the first two criteria is met. In addition, IRIS participants will be classified as diabetic in the presence of compelling indicators of hyperglycemia, even if requisite ADA testing is not performed. Specifically, patients will be classified as diabetic if any of the following three conditions is met:

- A physician diagnoses diabetes and prescribes an antidiabetic agent and one of the following test results is documented:
  - Fasting plasma glucose concentration equals or exceeds 126 mg/dl (7.0 mmol/L);
  - Random plasma glucose concentration equals or exceeds 200 mg/dl (11.1 mmol/L);
  - 2-hour OGTT glucose equals or exceeds 200 mg/dL (11.1 mmol/L);
  - HbA1c equals or exceeds 7.0%.
- Two fasting glucometer (capillary blood) glucose values obtained in a health-care setting (i.e., not a home test) equal or exceed 151 mg/dL (8.4 mmol/L) (i.e., 1.2 x 126 mg/dL [7 mmol/L]);
- Two random glucometer (capillary blood) glucose values obtained in a health-care setting (i.e., not a home test) equal or exceed 240 mg/dL (13.2 mmol/L) (i.e., 1.2 x 200 mg/dL [11 mmol/L]) in the presence of typical symptoms of hyperglycemia (e.g., polyuria, polydipsia, weight loss, blurry vision); In the situation where blood glucose levels are only available from a glucometer (capillary blood), it is acceptable to use these data, but only if the test is performed in a healthcare setting (physician's office, clinic, or skilled nursing facility), since proper standardization and use of the meter cannot be assumed with at-home testing. To be conservative, a margin of error of +20% has been incorporated, since the minimum acceptable accuracy for glucometer results is within 20% at glucose concentrations over 75 mg/dL.

A diagnosis of diabetes that is made during a hospital admission will not be recognized unless one of the following two conditions is met:

1. The hospital admission was for a diabetic emergency, such as diabetic ketoacidosis or hyperosmolar hyperglycemic syndrome;
2. The patient was discharged on any anti-hyperglycemic agent and a HbA1c  $\geq 7.0\%$  was obtained during the hospitalization.

### **All-Cause Mortality**

All-cause mortality will serve as a routine check on safety. It is also a very objective, additional measure of treatment effectiveness.

### **Cognitive Decline**

Decline in cognitive functioning will be measured as a change in mean score in the Modified Mini Mental State Examination (3MS). In a secondary analysis, we will restrict the analysis to participants who entered IRIS with a normal 3MS ( $>90$ ) and define a significant decline as an exit score below 78, the customary criterion for significant impairment. The reason to restrict this secondary analysis to participants with a normal baseline score is that any discrete change in score may have different importance for people with different baseline function. A fall of 12 points from normal to less than 78, however, is generally regarded as significant.

### **Severe Congestive Heart Failure**

CHF episodes that result in hospital admission or death will be counted in a combined secondary outcome (along with stroke and MI). The composite outcome was added at the request of the Data Safety and Monitoring Board (DSMB) to create a measurement of the net benefit of pioglitazone. Episodes of CHF are classified by members of the Cardiology Outcome Committee. In completing its assessment, the Committee will be guided by usual practices in diagnosing heart failure that require consideration of typical symptoms (shortness of breath, weight gain, edema, fatigue, dyspnea on exertion, PND), signs (weight gain, pulmonary rales, JVP, edema, tachypnea, tachycardia), test findings (e.g. pulmonary edema on chest radiography, serum BNP concentration) and alternative diagnoses. Non-fatal episodes of CHF leading to emergency room visits or hospital stays less than 24 hours in duration will not be counted as secondary outcomes. (All adjudicated episodes of CHF, regardless of severity or resultant hospitalization, are reported to the DSMB with other adverse events.)

## **B. Endpoints for Sensitivity Analyses Definitions**

### **Stroke: 2013 AHA/ASA Criteria for Stroke**

At the time the IRIS trial was initiated in 2004, it used a definition for stroke that was widely accepted at the time and based on clinical and imaging data (see section A above). The definition of stroke includes non-traumatic subarachnoid hemorrhage and intracerebral hemorrhage. To account for advances in science and technology, in 2013, the American Heart Association/American Stroke Association issued a Statement for Healthcare Professionals describing an updated definition for stroke. The update was motivated by opinion that the older, standard WHO definition had been made obsolete by evidence that permanent injury can result from events lasting less than 24 hours. In addition, the AHA/ASA felt that a uniform definition was needed for purposes of clinical care and research. The resulting new AHA/ASA definition for stroke broadly includes symptomatic and asymptomatic events caused by CNS infarction, intracerebral hemorrhage, subarachnoid hemorrhage, and cerebral venous thrombosis. There is also a category of “stroke, not otherwise specified” that is defined by an episode of acute neurological dysfunction presumed to be caused by ischemia or hemorrhage, persisting  $\geq$  24 hours or until death, but without sufficient evidence to be classified as one of the above.” The most significant feature of the AHA/ASA updated definition, and the only feature that affects IRIS, relates to the definition of ischemic stroke as “an episode of neurological dysfunction caused by focal cerebral, spinal, or retinal infarction.” The definition for CNS infarction is based on:

1. pathological, imaging, or other objective evidence of cerebral, spinal cord or retinal focal ischemic injury in a defined vascular distribution; or
2. clinical evidence of cerebral, spinal cord, or retinal focal ischemic injury based on symptoms persisting  $\geq$ 24 hours or until death, and other etiologies excluded (Note: CNS infarction includes hemorrhagic infarctions, types I and II).

Imaging evidence for infarction, according to the updated AHA/ASA criteria, includes findings from MRI or CT. The statement recognizes that MRI is more sensitive than CT scanning, particularly within first 12 hours, but that neither is perfectly accurate. This

updated definition, if applied to participants in the IRIS trial, would likely result in more events being classified as stroke compared with the original IRIS definition. This is because the original IRIS definition requires symptoms or signs to last at least 24 hours, even in the presence of imaging evidence for infarction. The updated definition classifies an episode of focal neurological dysfunction as an ischemic stroke if there is evidence for infarction regardless of duration of symptoms.

The updated definition for stroke caused by ICH (“Rapidly developing clinical signs of neurological dysfunction attributable to a focal collection of blood within the brain parenchyma or ventricular system that is not caused by trauma”) is identical to the IRIS definition, including the exclusion of subdural and epidural hematomas. The updated definition for stroke caused by SAH (“Rapidly developing signs of neurological dysfunction and/or headache because of bleeding into the subarachnoid space {the space between the arachnoid membrane and the pia mater of the brain or spinal cord}, which is not caused by trauma.”) is also identical to the current IRIS definition.

The ancillary analysis for the primary outcome will define fatal and non-fatal stroke according to the AHA/ASA updated definition for stroke and represents a sensitivity analysis to show readers how our findings are affected by use of the more modern definition. It is important to note that the primary outcome for the IRIS trial (i.e., fatal or non-fatal MI plus fatal or non-fatal stroke) does not change and will still be classified and reported using the original IRIS protocol and its older stroke definition. However, the sensitivity analysis will be reported to show the effect of the new criteria on IRIS findings.

